## **2.2. SECONDARY OBJECTIVES AND ENDPOINTS**

### **2.2.1. Secondary objectives**

The interest of web-application monitoring will also be assessed in terms of:

- progression-free survival,
- overall patient survival at 2 years,
- estimated time between the diagnosis of a complication, allowed by the application, and the theoretical date of the scheduled subsequent follow-up,
- proportion of hospitalization for life-threatening emergencies,
- total number of complications observed,
- quality of life of patients,
- the degree of patient compliance with the use of the web application
- the degree of satisfaction with the use of the web-application and the implementation of web-monitoring,
- number of significant complications whatever they may be (but defined above), which have arisen and not identified via the application (sensitivity calculation),
- number of significant complications whatever they may be (but defined above), which have arisen and identified in the systematic follow-up group, excluding systematic follow-up,
- Performance Status at relapse,
- description of health consumption in the 2 groups.

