### **2.2.2. Secondary endpoints**

Progression-free survival is defined as the time between the date of the first examination making the diagnosis of partial response or complete response and the date of consultation allowing the diagnosis of the relapse.

The diagnosis of partial or complete response, as well as relapse in this study follows the definition of the Cheson criteria.

The time between the date of diagnosis of the relapse and the nearest consultation date scheduled as part of the standard follow-up will be evaluated. The same will be done with the date of diagnosis of significant complications.

The time taken to set up a treatment will also be evaluated. Thus, the time between the date of diagnosis of each event and the date of implementation of the care (1st psychological consultation, date of D1 of treatment, etc.) will be evaluated.

Overall survival is defined as the time between the date of diagnosis of the complete or partial response as defined in chapter 2.1.2 and death from any cause within 2 years.

Quality of life will be studied using the QLQ-C30 and HUMEUR PhQ9 questionnaires at inclusion and then follow-up consultations at 3, 6, 9 and 12 months.

Patient compliance with the use of the web application will be assessed based on the number of assessments completed by patients; an evaluation every 14 days is expected. Patients who have completed less than 1 assessment per 42 days (6 weeks) will be considered non-compliant. An overall compliance rate over the entire period and a rate per 14-day period can then be presented.

The satisfaction and feelings of patients with regard to the web-monitoring and the use of the web-application will be assessed by a self-questionnaire during the follow-up visit in the 6th month.

The calculation of the application's sensitivity is based on the evaluation of the number of alerts triggered by the application against the results of systematic or alert-triggered imaging examinations.

CONFIDENTIAL

The Performance Status will be assessed according to WHO recommendations.

The description of health consumption will be assessed by the number of consultations, imaging and laboratory tests performed by the patients in each group.

[figure not shown]

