## **5.6. RULES FOR SUBJECT WITHDRAWAL**

### **5.6.1. Criteria for a study subject's early withdrawal**

Patients can withdraw their consent and request to withdraw from the trial at any time and for any reason, without losing the right to be treated by their doctor. The investigator may also prematurely discontinue a patient's participation in the trial for any reason that would serve the best interests of the patient, including the case of an intercurrent disease or an adverse event. In the event of premature discharge, at any time and for any reason, the investigator should notify the patient, if necessary, and document the reasons as fully as possible.

Test exits must be reported in particular for the following possible reasons:

- Death,
- Withdrawal of consent with the patient's request not to use the data already collected,
- Wrongly included,
- Choice of investigator,
- Patient choice,
- No seizure in the application for 6 consecutive weeks apart from a pathology or relapse preventing seizure,
- Lost view.

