## **6.2. STATISTICS**

### **6.2.1. Description of planned statistical methods**

This study should allow us to evaluate the functioning of the application in a follow-up context in patients with lymphoma at high risk of relapse.

The patient sample for this analysis will consist of all patients, included in the study and meeting all the eligibility criteria described in Chapter 4, who have signed a consent.

The initial characteristics of the analysis population (demographic data, disease, previous and concomitant treatments, prognostic factors, etc.) and all the evaluation criteria described in paragraph 2 will be presented globally

For the qualitative variables, we will present the number as well as the percentage. For quantitative variables, we will present the median or the mean plus or minus the standard deviation depending on the normality of the variable, the minimums and maximums will also be indicated.

Events, as defined in chapter 2.1.2. (apart from relapse) will be described in terms of frequency by etiological type (HLT or HLG T according to the MedDRA classification) and by severity according to NCI CTCAE v4.02.

For the analysis of the censored data (overall survival and other timeframes of events), the survival curves will be plotted according to the Kaplan-Meier estimates, the medians of survival will be presented as well as their 95% confidence intervals.

For performing multivariate survival analyzes, the semi-parametric Cox model will be used to calculate the odds ratios which will be presented with their 95% confidence interval.

The sensitivity of the application to detect a relapse and / or significant complications will be calculated.

Quality of life scores will be calculated according to EORTC guidelines for the QLQ-C30. The quality of life will be described at each measurement time and compared to inclusion and then studied longitudinally using mixed analysis of variance models for repeated measures.

PHQ9 scores will be calculated according to the recommendations, described at each measurement time and compared to inclusion. The classes proposed in the literature ( $\leq 4$ ; 5-14;  $> 14$ ) will be used to describe the state of depression of patients.

The analyzes will be carried out with SAS 9.3 software (SAS Institute Inc. Cary, NC, USA).

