## ***7.3. MODALITIES AND DURATION OF THE FOLLOW-UP OF PERSONS FOLLOWING THE OCCURRENCE OF ADVERSE EVENTS***

All the patients included in the study are followed for 2 years (24 months).

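### Health consumption and total complications are planned as counts with no time window or time-on-study denominator, so unequal exit from the study can shift the between-arm comparison when the underlying rates are equal

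*Combined protocol and SAP*

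**What the plan says.** - **Health consumption (Section 2.2.2).** "The description of health consumption will be assessed by the number of consultations, imaging and laboratory tests performed by the patients in each group". No period is attached.
- **Complications (Section 2.2.1).** One secondary objective is the "total number of complications observed". Again no period is attached.
- **Summary method (Section 6.2.1, Description of planned statistical methods).** "For quantitative variables, we will present the median or the mean plus or minus the standard deviation depending on the normality of the variable". Events "will be described in terms of frequency by etiological type" and by severity grade.
- **Incomplete follow-up (same section).** The only methods offered are for times to an event: "For the analysis of the censored data (overall survival and other timeframes of events), the survival curves will be plotted" by Kaplan-Meier, with a Cox model for multivariate analyses. Neither handles a count.
- **Planned follow-up (Section 7.3).** 24 months for every included patient.
- **Early exit (Section 5.6.1).** "Test exits must be reported in particular for the following possible reasons". The list includes death, loss to follow-up, patient choice, investigator choice, and six consecutive weeks with no entry in the application unless illness or relapse prevents it. Only the web-application arm uses the application, so only that arm can meet the last reason.
- **After exit (Section 5.6.2).** Care follows usual practice outside the protocol. Continued collection of resource use or complications is not mentioned.

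The plan standardises for time in one place only: Section 2.2.2 gives compliance as a rate per 14-day period.

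**The concern.** A count grows with the time over which it is collected. A patient who leaves at month 6 of 24 has had a quarter of the planned time in which to accrue visits, tests, scans and complications, yet enters the group total or mean like a patient seen for the full period. Using per-patient means or medians, as Section 6.2.1 allows, does not remove this.

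Unequal time on study is plausible here for two reasons that pull in opposite directions. The no-entry exit can shorten follow-up in the web-application arm only, which would lower that arm's counts. Sections 1.4 and 1.5.3 hope for better survival with the application, which would lengthen follow-up in that arm and raise its counts.

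At stake is how the description of use and complications in the two groups is read. Sections 1.5.1.2 and 1.5.3 present less imaging and lower follow-up cost as an expected collective benefit, and readers will look to these counts for evidence of it.

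**Working it through.** **Figures in the plan.** The plan states no numerical target, exit rate or death rate for these two endpoints, so there is no figure to reproduce. From the documents I use the 24-month follow-up, the visit schedule (Section 5.3), the maximum of 40 patients per group and the 6-month primary evaluation (both in Sample size determination). All exit and survival percentages below are assumptions.

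**1. One patient.** Section 5.3 schedules eight visits and eight biology reports after baseline (M3 to M24) in each arm, and four scans after baseline (M6, M12, M18, M24) in the standard arm. A patient who leaves just after M6 supplies 2/8 = 25% of the scheduled visits and, in the standard arm, 1/4 = 25% of the scheduled scans.

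**2. Exit in the web-application arm only.** Suppose a fraction x leaves at month m, nobody leaves the standard arm, and no data are collected after exit. The web-arm share of full person-time is

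(1 - x) + x·m/24.

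| x | m | Share of person-time | Fall in count at equal rates |
|---|---|---|---|
| 0.10 | 6 | 0.90 + 0.025 = 0.925 | 7.5% |
| 0.10 | 3 | 0.90 + 0.0125 = 0.9125 | 8.75% |
| 0.30 | 6 | 0.70 + 0.075 = 0.775 | 22.5% |
| 0.30 | 3 | 0.70 + 0.0375 = 0.7375 | 26.25% |

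**3. Exit in both arms.** With a constant exit hazard and a fraction p gone by 24 months, mean time on study is 24·p / [-ln(1 - p)] months. This gives 22.78 months for p = 0.10, 21.51 for 0.20, 20.19 for 0.30 and 18.79 for 0.40. For 40 patients that is 75.9, 71.7, 67.3 and 62.6 patient-years, against 80.0 with no exits. With equal true rates, the ratio of raw counts is the ratio of mean times:

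| Exits, higher arm vs lower arm | Raw-count ratio | Rate ratio |
|---|---|---|
| 20% vs 20% | 21.51/21.51 = 1.00 | 1.00 |
| 20% vs 10% | 21.51/22.78 = 0.94 | 1.00 |
| 30% vs 10% | 20.19/22.78 = 0.89 | 1.00 |
| 40% vs 20% | 18.79/21.51 = 0.87 | 1.00 |
| 40% vs 10% | 18.79/22.78 = 0.825 | 1.00 |

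In the last row, a true rate 20% higher in the arm with more exits would appear as 1.2 × 0.825 = 0.99, that is, as no difference.

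**4. Survival difference.** If 24-month survival were 80% in one arm and 60% in the other (constant hazard), mean exposure as a share of 24 months would be 0.20/0.223 = 0.896 and 0.40/0.511 = 0.783. At equal rates the longer-lived arm's count would be 0.896/0.783 = 1.14 times the other's. This moves the comparison the opposite way from step 2 if the survivors are in the web-application arm.

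**5. Shorter window.** If complications were counted over 6 months, the period used for the primary objective, the exits in step 2 would leave (1 - x) + x·m/6 of person-time: 1.00 for m = 6, and 0.95 or 0.85 for m = 3 with x = 0.10 or 0.30. The gap is then 0 to 15%. The unstated window thus matters in itself.

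**The case against.** **Descriptive endpoints.** Health consumption is the last of twelve secondary objectives and is framed as a description. Section 6.2.1 plans no test on it and says the evaluation criteria will be presented globally. No decision rule uses it. This stands and limits the importance of the point. It does not remove it, because Sections 2.2.1 and 2.2.2 still ask for the description by group, and a side-by-side description will be read as a comparison.

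**Follow-up may continue after exit.** Section 7.3 follows all included patients for 24 months, and Section 5.6.3 says that in all cases patients are followed to the 24-month visit. But the first sits under adverse-event follow-up and the second concerns early termination of the study as a whole. Neither says that use is recorded after an individual exit. What stands is that loss of data after exit is an inference from silence. If collection continues, the no-entry rule causes no distortion, and only death and true loss remain.

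**The imaging contrast is designed.** Scheduled scans occur only in the standard arm, so a lower web-arm scan count is expected whatever the exits. This is correct; the exposure effect adds to that contrast and does not create it. Visits and biology share one schedule in both arms.

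**More use by longer survivors is real use.** Total use per randomised patient is a legitimate measure of burden, and a reader might infer from step 4 of the working that the 1.14 is simply spurious. The documents do not support that: they do not say whether a rate or a total is wanted. Both should be shown.

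**A split at relapse.** Separating surveillance use from use after relapse is attractive, because Section 5.4 keeps patients on the application during relapse treatment. But the relapse date falls after randomisation and is one the application is meant to bring forward, so the split carries its own bias.

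**Conclusion.** The omission is real. Nothing in the protocol supplies a time window, a denominator or a treatment of death for these counts, and the listed exits allow time on study to differ between arms. Under that condition the planned summaries can show less or more use, or fewer or more complications, when the rates are equal.

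A reader might go further and conclude that exits will make the web-application arm look cheaper or safer. The documents do not support that: distortion needs unequal time on study, its direction depends on whether non-entry exits or survival dominate, and equal exits leave the ratio at 1.00. Nor do they support treating reduced cost as a trial objective; it appears only in the rationale.

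The 7.5-26% is illustrative. It rests on assumed web-arm exits of 10-30% at months 3-6, none in the standard arm, a 24-month window and no data after exit. The primary endpoint, alpha and the 40 patients per group are unaffected.

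**What to change.** 1. State the time window for each count, and whether collection continues after individual exit.
2. Report time on study and exit reasons by randomised arm.
3. Alongside the raw totals, report consultations, imaging, laboratory tests and complications as rates per patient-month by arm, with a rate ratio and 95% CI (Poisson with robust variance, or negative binomial, with log person-time as offset).
4. Because a rate while alive does not settle the effect of death, also give the mean cumulative count to M24 by arm with death as a terminal event.
5. Make any split into use before and after relapse supplementary, labelled descriptive, with the reason given.

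**Cost.** A paragraph of analysis text and modest extra programming; no change to design or sample size. Relapse and death dates are already needed for the survival endpoints. Section 5.6.1 requires exits to be reported with reasons but does not mention dates, so the e-CRF should be checked for exit dates. Items 4 and 5 also need a date for each consultation, scan, test and complication; for consultations, scans and tests, Section 2.2.2 mentions only numbers.

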### 3. STUDY DESIGN

#### 3.1. STUDY METHODOLOGY

This research is a cohort study, aimed at evaluating the value of web-application monitoring for the detection of relapses, and of any other event justifying medical treatment, in patients treated for partial response lymphoma. or complete.

It is a multicenter, prospective, longitudinal and randomized study.

#### 3.2. STUDY SCHEMA

## **4. STUDY POPULATION**

The population concerned includes all patients with lymphoma at high risk of relapse, in follow-up for this cancer and having access to the Internet.

We plan to include 80 patients over a 48-month period.

### ***4.1. INCLUSION CRITERIA***

- 1) Patient with either:
  - a. T-cell lymphoma in first complete or partial response
  - b. Hodgkin lymphoma in 2nd complete or partial response including after autograft
  - c. c. Large B-cell diffuse lymphoma in 2nd complete or partial response including after autograft
- 2) End-of-treatment imaging in the last 4 weeks
- 3) Age  $\geq$  18 years
- 4) PS  $\leq$ 2 (WHO)
- 5) Patient with an initial symptoms score less than or equal to 5
- 6) Patient with internet access and mailbox
- 7) Patient affiliated to a social security scheme
- 8) Patient with written consent prior to any procedure specific to the study

### ***4.2. NON INCLUSION CRITERIA***

- 1) Patient whose lymphoma progressed at the end of the specific treatment (evaluation <3 months after the end of the previous treatment)
- 2) Symptomatic brain or meninges localization
- 3) Presence or history of another cancer in the last 3 years, except skin cancers (other than melanoma), in situ cancers of the cervix or other cancers considered cured
- 4) Persons deprived of their liberty or under trusteeship
- 5) Dementia, mental impairment or psychiatric pathology that may compromise the informed consent of the patient and / or compliance with the protocol and follow-up of the study
- 6) Patients who cannot follow the protocol for psychological, social, family or geographical reasons,
- 7) Pregnancy or breast-feeding
- 8) Patient participating in another interventional study

## **5. STUDY DESCRIPTION**

### **5.1. *BASELINE***

Patients eligible for the trial will be required to sign a consent to participate. A patient who has already been included in the study cannot be included a second time in the event of a new response to the treatment implemented.

For the initial inclusion assessment, certain examination results (extension assessment for a given pathology) carried out prior to signing the consent may be used if they were done within the time limits requested in the protocol.

#### **5.1.1. Clinical assessment**

It includes a complete clinical examination (within 2 weeks prior to inclusion) with:

- the history of the disease,
- the evaluation of weight and PS,
- the calculation of the initial score,
- completion of the QLQ-C30 and PhQ-9 quality of life questionnaires.

#### **5.1.2. Imaging assessment**

It should be less than 4 weeks old at the time of inclusion and start of surveillance and includes a thoraco-abdomino-pelvic (TAP) at least (cervical at best) and / or a PET scan.

## **5.2. *STUDY EVALUATIONS***

The type of follow-up the patient will benefit from will be assigned by randomization.

Patients will be able to benefit from the supportive care adapted to their situations. The need for this supportive care can be detected during consultations or through the application.

All patients will be seen in consultation every 3 months with a clinical examination including estimation of the PS and a biological assessment (according to the clinician's habits).

The questionnaires (QLQ-C30 and PhQ-9) will be completed again at the 3,6-,9- and 12-month follow-ups.

For patients randomized to the "standard" arm, a systematic imaging workup (minimum TAP CT (cervical at best)) will be performed every 6 months corresponding to standard follow-up.

Patients randomized to the "Web-application follow-up" arm will perform a self-assessment of symptoms via the Moovcare application with a maximum interval of 14 days between 2 seizures, and if necessary, each time symptoms appear.

In the event of a Moovcare alert (and telephone call to the patient) suggesting a relapse or a complication, a CT scan and / or other evaluation examination (PET, biopsies, etc.) will be scheduled within ideally less than 14 days depending on the type of alert.

CONFIDENTIAL

To be able to connect to the application, included patients will receive personal access codes to the application by email with instructions for use:

- access to the application is via a username and password,
- the password is encrypted in the host's database,
- access to the application is via a secure SSL connection (https) which is a protocol for securing data exchanges between the client and the application server,
- a brute force intrusion detection system makes it possible, when too many connection attempts are detected, to deactivate the account in question.

A satisfaction questionnaire will be taken at the 6-month follow-up.

### 5.3. SCHEDULE OF THE STUDY

*For patients randomized to the “standard” arm:*

	Baseline	M3	M6	M9	M12	M15	M18	M21	M24
Eligibility criteria	X								
Study presentation / Written inform consent	X								
Cancer history	X								
Physical exam (PS, weight)	X (- 15 days)	X	X	X	X	X	X	X	X
Biology report (parameters at the discretion of the investigator)		X	X	X	X	X	X	X	X
Initial Symptom score	x								
Imaging assessment	X (- 4 weeks)		X		X		X		X
Quality of life questionnaires	X	X	X	X	X				

*For patients randomized to the “web-application follow up” arm:*

	Inclusion	M3	M6	M9	M12	M15	M18	M21	M24
Eligibility criteria	X								
Study presentation / Written inform consent	X								
Cancer history	X								
Physical exam (PS, weight)	X (- 15 days)	X	X	X	X	X	X	X	X
Biology report (parameters at the discretion of the investigator)		X	X	X	X	X	X	X	X
Initial Symptom score	x								
Self assessment	Every 14 days maximum for patients included in the “web application follow-up” arm								
Imaging assessment	X (- 4 weeks)	In the event of a Moovcare alert or clinical call point							
Satisfaction questionnaire			X						
Quality of life questionnaires	X	X	X	X	X				

CONFIDENTIAL

## 5.4. MOOV CARE WEB-APPLICATION FOLLOW-UP MANAGEMENT

The investigator can regularly consult the history of the SENTINEL application.

In the event of a "suspected" relapse (depending on the answers to the questions), an alert email will be sent to the investigator.

In addition, an email will be systematically sent to the investigator if the free text window is filled in by the patient. If the symptoms appear not to be serious, the response will be optional, the patient being informed of this possibility. If there is any doubt, the investigator will call the patient or even summon him.

[figure not shown]
In the event of a SENTINEL alert, the investigator should:

- 1) consult the history of symptoms,
- 2) call the patient to verify the absence of entry errors, the absence of a low-calorie diet in case of weight loss, and ask the patient about his symptoms
- 3) if the doubt is confirmed, summon the patient as soon as possible (ideally <14 days) with an initial TAP CT (and cerebral if suggestive clinical signs).

For the most significant symptoms, supportive care may be offered, for example:

- if persistent pain: consultation of algology,
- if weight loss of 3 kg or more and / or anorexia: dietician advice,
- if dyspnea: pneumologic opinion
- if depression: psychologist / psychiatrist advice / psychotropic treatment.

